- a. Change in patient willingness to repeat BTX-A injection procedure as assessed with an 11-point visual analog scale.
- b. Change in discomfort in patients that undergo BTX-A injection, measured using the Numeric Pain Scale scores provided by patient prior to and following the treatment procedure.
- c. Change in Patient Global Impression of Improvement score provided 6 weeks post-procedure.

Secondary endpoints:

- a. Change in procedure times (from cystoscope insertion to removal).
- b. Change in International Consultation on Incontinence Questionnaire-Urinary Incontinence Short Form.
- c. Change in Neurogenic Bladder Symptom Score – Short Form

Safety endpoints:

- a. Incidence of symptomatic UTI within the first 4- 6 weeks after the procedure.
- b. Incidence of bleeding requiring admission or hospital/office evaluation related to the injection procedure.
- c. Rate of bothersome incomplete bladder emptying requiring de novo catheterization within the first 4-6 weeks.

Demographic data: collected from the EMR for secondary analysis

- Age
- Gender/sex
- Race
- Body mass index (BMI)
- Diagnoses at the time of procedure – nature of neurogenic bladder
- Is the patient naive to BTX-A or not
- Number of total BTX-A procedures
- Past medical history
- Past surgical history

- Chronic narcotic use
- 3 or more symptomatic UTI in the last year
- Current Anticoagulation use
- Other GU relevant medications
- Mode of bladder emptying? Spontaneous voiding, CIC, Foley, SPT
- History of bladder augmentation?
- History of bladder outlet procedures
- Was anticoagulation stopped for the procedure?

Sample size and power calculation: Sample size was calculated by powering the primary outcome (11-point visual analog scale for willingness to repeat the procedure, Range: 0-10) between the two study arms. A continuous model was utilized. Cohen effect sizes were used with a power of 80% with statistical significance defined as an alpha of 0.05 for a target sample size of 74 patients. Accounting for a 5% drop out rate, our final target sample size will be 78 patients split between the two study groups (please see the randomization plan below).

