Recruitment: Individuals with the diagnosis of OAB symptoms (frequency, urgency, UUI) who do not have a painful bladder condition and scheduled to undergo 200 or 300 units of intradetrusor BTX-A will be identified through the electronic medical record (EMR). The dosing amount will be determined by the physician who is indicating the patient for the BTX-A treatment based on clinical picture and is not influenced in any way by this study. We will recruit and sample from patients who are already scheduled for this therapy prior to study enrollment. Patients who meet inclusion criteria will be approached on the day of the procedure and consented in person if they are interested in participating.

5. Study Intervention

The study will include a clinic visit for the Botox procedure, a scheduled follow-up visit, and possibly a 15-minute phone call approximately 6 weeks after Botox injection.

During the clinic visit, the patient will rate the patient's willingness to repeat the procedure and pain level and fill out a short questionnaire called the International Consultation on Incontinence Questionnaire-Urinary Incontinence Short Form (ICIQ-UI SF) and Neurogenic Bladder Symptom Score-Short Form (NBSS-SF). At the follow-up visit, the patient will fill out the ICIQ-UI SF and NBSS-SF again to assess symptom improvement, Patient Global Impression (PGI) of Improvement score, and assess the patient's willingness to repeat the procedure. The questionnaire should take roughly 5 minutes to fill out. The component of the patient's participation that is being researched is the patient's willingness to repeat the procedure, response to questionnaires, and clinical response to the Botox. In addition, if the patient participates in the study, data from the medical record will be collected for this research. Types of data collected include demographic and baseline characteristics, procedural time, procedural response, discomfort with the procedure, and any procedural complications encountered. Besides 4-6 weeks follow-up, patients charts will retrospectively reviewed at the 6-12 months **At 6 months to 1 year after their Botox injection, to see if additional therapies were pursued.**

Intervention	Procedure visit	Post-procedure visit (4-6 weeks after procedure visit)	12 months after procedure visit
Sign consent form	X		
ICIQ-UI SF Questionnaire	X	X	
NBSS-SF	X	X	
PGI score		X	
Numeric Pain Rating Scale	X		
Willingness to repeat procedure scale	X	X	
Randomization	X		

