- Diagnosis of bladder pain syndrome or other chronic pain syndrome including fibromyalgia, chronic pelvic pain, pelvic floor dysfunction, levator myalgia.
- Untreated bladder malignancy.
- Women who are currently pregnant or breast feeding.
- Contraindications to intradetrusor BTX-A injections.

11. Screening and Recruitment ^{S R}

All patients scheduled to undergo injection of 200 or 300 units of intradetrusor BTX-A for all indications other than bladder pain syndrome will be identified through the electronic medical record (EMR). A trained, primary member of the research team will identify all patients scheduled for BTX-A as listed on the EPIC schedule for the Urology providers listed above: [name], [name], [name], and [name]. Without opening charts, a note can be placed on the schedule for patients >18 yo to be evaluated for study qualification. The physician caring for the patient on the day of their scheduled BTX-A procedure will identify whether the patient meets inclusion/exclusion criteria for study enrollment based on the criteria listed in this protocol (inclusion and exclusion criteria are listed in the Study Population section above). By this process, the patients' information in the EMR will only be accessed by primary medical team members and will only be accessed by study team members after patients agree to enroll.

These patients will be approached on the day of the procedure and consented to in person if they are interested in participating. Other than a detailed consent form, no recruitment materials or advertisements will be utilized as part of this study.

12. Withdrawal of Subjects

Subjects would be withdrawn from the study if they are found to have symptomatic

urinary tract infection on the day of the procedure – this would be defined by symptoms such as dysuria, frequency or urgency above baseline, or hematuria along with a urine dip that is positive for nitrites or leukocyte esterase.

- Subjects would be withdrawn if they are not able to tolerate the procedure itself and it is terminated prior to full injection of reconstituted BTX-A or if BTX-A was not able to be injected for other reasons (difficult anatomy, unable to pass scope or perform in the office)

13. Provisions to Protect the Privacy Interests of Subjects

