Informed consent will be obtained from a member of the research team on the day of the BTX-A procedure. Patients undergoing intradetrusor BTX-A within the Urology offices at HMH TMC, West, Willowbrook, or Sugarland, will be identified the week prior and all subjects meeting criteria for inclusion will be approached about participation on the day of their scheduled procedure. If the subject fulfills inclusion criteria, the study team member (attending, fellow, research coordinator) will discuss the goal of the study and the process of BTX-A reconstitution and injection. If the patient is interested, the study requirements will be explained in detail - including requirements on the day of the procedure (short questionnaire, NPS rating prior to and after procedure) and 4 weeks follow up telephone call. The patient will be given appropriate time to answer any questions she may have related to the study. Written information will be provided, and the physician will allow adequate time for the subject to reflect following this discussion.

If the patient agrees to participate, they will be consented in person by a member of the research team and will then be randomized. These documents will be safely stored

as discussed above.

A copy of the consent will be retained by the research coordinator in a locked file cabinet, and one copy will be given to the patient.

19. **Waiver of Informed Consent and /or Authorization**

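### Section 12 withdraws randomised patients whose procedure is stopped for intolerance, and the text neither continues their follow-up nor keeps their scores in the analysis

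*Combined protocol and SAP*

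**What the plan says.** Section 18 gives the order of events. Once a patient agrees, "they will be consented in person by a member of the research team and will then be randomized". This happens on the day of the procedure.

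Section 12 then sets the withdrawal rule: "Subjects would be withdrawn if they are not able to tolerate the procedure itself and it is terminated prior to full injection". The same sentence also withdraws patients in whom the toxin could not be injected because of anatomy, failure to pass the scope, or inability to perform the procedure in the office.

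The first two primary endpoints in Section 4 are "Change in patient willingness to repeat BTX-A injection procedure as assessed with an 11-point visual analog scale", which is the endpoint used for the sample size, and "Change in discomfort in patients that undergo BTX-A injection, measured using the Numeric Pain Scale scores". Section 18 describes the pain measurement as "NPS rating prior to and after procedure". The third primary endpoint is the "Patient Global Impression (PGI) of Improvement score" taken at follow-up. The Section 5 schedule places the pain scale at the procedure visit, willingness at the procedure visit and at 4-6 weeks, and PGI-I at 4-6 weeks.

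On losses, Section 4 says: "Accounting for a 5% drop out rate, our final target sample size will be 78 patients".

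**The concern.** The trial asks whether fewer injections are easier to tolerate and make patients more willing to return. A patient who cannot finish the assigned schema is among the most informative on both questions. If such patients drop out of the comparison, it is made among those who tolerated their arm and no longer between the groups as randomised. A dropout allowance protects the number of patients; it does not protect against loss related to the outcome.

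The matter is time-critical. Same-day and 4-6 week scores that are never collected cannot be recovered by a later choice of analysis.

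**Working it through.** **1. Is the withdrawal after randomisation?** Yes. Section 18 randomises after consent, and the arm fixes the number of injections, so it must be known before the first one. A procedure stopped part-way is stopped after assignment.

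**2. Does other text fill the gap?** These are the candidates:
- Section 4 commits to CONSORT but defines no analysis set and does not say how the commitment applies to withdrawn patients.
- Section 5 lists discomfort and procedural complications among the data collected, and its schedule makes no exception for stopped procedures. It does not mention withdrawn patients.
- Section 8 sets a 6-year minimum for keeping records. That is storage, not analysis.
- Section 16 provides phone contact for a missed follow-up survey, without saying that it covers withdrawn patients.

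There is no intention-to-treat or per-protocol definition, and no rule for missing data or replacement.

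**3. The plan's own figure.** 74 / 0.95 = 77.9, rounded up to 78, so the stated total reproduces. It has no slack: 78 x 0.95 = 74.1.

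**4. Implied effect size.** Section 4 gives no numeric effect size, SD or sidedness. Assuming equal arms (37 each), a two-sided 0.05 test and 80% power, the normal approximation gives d = (1.960 + 0.842) x sqrt(2/37) = 0.65, and the t test gives 0.66. A one-sided test would give 0.58. With 39 per arm and d = 0.66, power is 82%.

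**5. Illustration of selective loss.** The assumptions are: 39 per arm; normal scores with SD 1; a true difference of 0.66 SD in the post-procedure score in favour of 5 injections; and removal of the two least tolerant patients from the 20-injection arm only. Tolerance has correlation r with the score. The documents give neither a termination rate nor r, so r is varied.

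The two lowest of 39 standard normal values average -2.15 and -1.74, which sum to -3.89. Removing those patients raises the mean of the remaining 37 by r x 3.89/37 = 0.105r. The observed difference becomes 0.66 - 0.105r:

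| r | Difference (SD) |
|---|---|
| 0.2 | 0.66 - 0.021 = 0.64 |
| 0.5 | 0.66 - 0.053 = 0.61 |
| 0.8 | 0.66 - 0.084 = 0.58 |

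At r = 0.5, simulated power is about 75%. Losing two patients at random from the same arm leaves 0.66 SD and about 81% power, so most of the fall comes from selection and not from the smaller number.

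**6. Direction.** Equal losses cancel: one from each arm leaves 0.66 SD and about 82% power. Two lost from the 5-injection arm instead give 0.66 + 0.053 = 0.71 SD at r = 0.5. Direction also depends on which two ratings define change in willingness, because Section 5 does not say whether the procedure-visit rating comes before or after injection.

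**The case against.** The strongest objection is that exclusion is inferred. The infection rule in Section 12 says the patient is withdrawn from the study, whereas the intolerance rule says only that the patient is withdrawn. That leaves room for withdrawal from treatment alone. The schedule and data list in Section 5 make no exception for stopped procedures, so same-day scores might be taken anyway. The consent form is not part of the text reviewed here and could address data after withdrawal. All of this stands. It makes exclusion the natural reading and not an established fact, but it does not supply the missing statement.

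Terminations may also be few. Section 6 describes the therapy as typically well tolerated, Section 10 excludes chronic pain syndromes, Section 14 provides local anaesthetic, and Section 13 calls both schemas standard office practice. This stands too, and it limits the likely size.

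The illustration depends on its assumptions, especially r and the one-sided pattern of loss. For that reason it is given as a range and carries little of the argument.

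Finally, patients who were never injected are a different case. The discomfort endpoint is worded for patients who undergo injection, and a patient with no injection has no completed procedure to be willing to repeat. Handling them separately is defensible, and the point here does not rest on them.

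A reader might infer that the plan definitely discards these patients, or that the result will be biased towards one schema. The documents support neither: they do not say what happens to the scores, they give no termination rate by arm, and they do not link intolerance to the number of injections.

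**Conclusion.** The point holds as a gap attached to a stated rule. Confidence is high that the rule operates after randomisation, that its trigger lies close to two primary endpoints, and that the text available does not say whether the affected patients are scored, followed or analysed. Confidence does not extend to the presence, direction or size of any bias.

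The illustrated effect is modest: 0.02 to 0.08 SD off a difference of 0.66 SD for two one-sided losses, and none when losses are equal. It assumes equal allocation, a two-sided test, a back-solved effect size and normal scores. It is not a forecast. The change is worth making because it costs little and the uncollected scores would be irrecoverable.

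**What to change.** In Section 12, separate stopping the procedure from leaving the study, and leave the decision to stop as it is. For patients whose procedure is started and then stopped for intolerance:
- collect the scheduled same-day pain and willingness scores, and the 4-6 week willingness and PGI-I scores, by phone if needed;
- include these patients in their assigned arm in the primary analysis.

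Add a sensitivity analysis restricted to completed procedures, and report non-completion by arm and reason. Patients in whom no injection was attempted because of anatomy, scope or office reasons may be handled by a separate stated rule, with counts reported by arm.

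The cost is protocol wording, a few more follow-up contacts and a few more of the $50 follow-up payments in Section 16. The scales are already scheduled, and phone contact for missed surveys is already planned. The downside is slight dilution of the effectiveness comparison by partly treated patients, which the completed-procedure analysis would show.
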